6.4.5 Assessment of primary and secondary efficacy endpoints

The primary endpoint is defined as the proportion of randomised patients with recurrent AF (AF episode lasting > 7 days) within 12 months, but outside of the initial 6-week blanking period (see section 8.1.2).

Secondary endpoints to be described are:

- Proportion dying within 12 months
- Proportion with hospital admission for any reason within 12 months
- Proportion with procedural-related complications defined as any AE that is deemed at least possibly related to intervention
- Proportion with bleeding events within 7 days of procedure
- Proportion with repeat procedures (any additional procedure for AF after the baseline index trial procedure(s)) within 12 months
- Change in ejection fraction from baseline at 12 months
- Proportion with clinical success of procedure
- Change in QoL at 12 months, as measured by SF-12 and AF-PROMS
- AF burden by 12 months
- Anti-arrhythmic drug use.

Clinical success will be defined as a 75% or greater reduction in the number of AF episodes as measured by the Reveal LINQ implant device within 12 months, but outside of the initial 6-week blanking period.

Change in QOL will be measured by the change in AF-PROMS summary scores and SF-12 PCS and MCS between screening and 12 months. SF-12 scores will be calculated as described in the appendix supplementary table 2³.

AF burden will be defined as the proportion of time in AF over the 12 months but outside of the initial 6-week blanking period, as measured by the Reveal LINQ implant device.

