6.5 Level of significance

No hypothesis testing will be done for this pilot study.

For efficacy outcome measures we will use 80% one-sided confidence intervals to give an indication of whether the endpoint is likely to be of interest, an approach described by Cocks et al. for pilot trials⁴.

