7.1 Study period and visit definitions

7.1.1 Visits

Patients will be identified as suitable for the study by their usual clinical care provider. Patients referred for DC cardioversion or management of persistent AF will be screened for inclusion into the trial. Patients will give informed consent in pre-admission. Baseline characteristics, quality of life and symptom measures will be assessed at this point.

On the day of the procedure patients will be randomised to DCCV or Pulmonary Vein Isolation plus DCCV. LINQ will be inserted during the procedure. Patients will be followed up at 6 weeks by telephone for quality of life and symptom measures.

Patients will return to the clinic at 3 months (clinical follow-up, 12 lead ECG, repeat QOL and symptom measures) and at 12 months (clinical follow-up, 12 lead ECG and symptoms). Monthly remote interrogation of the loop recorder will measure burden of AF (time in AF) and duration of episodes.

[figure not shown]
Patients who consent will remain within an observational registry for 5 years following the end of the trial. This long-term passive follow-up will track patient mortality and clinical status from

ORBITA-AF Pilot Trial: Statistical Analysis Plan

routinely collected clinical data. No intervention or investigations will be performed as part of this long term follow up.

Data from this pilot study will be analysed at 12 months to allow assessment of feasibility for a larger trial, and patients who complete the 12-month follow-up visit and consent will continue in registry follow-up for 5 years post procedure.

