7.4 Treatment assignment and treatment groups

Patients will be randomised on a 1:1 basis to either DCCV alone or DCCV + PVI. Block randomisation is used with randomly varying block sizes of length 2, 4, and 6. Randomisation will not be stratified by any factors. The allocation algorithm is written by the study statistician using R (randomizeR package). Details of the randomisation method and validation details are stored in a separate document which can be accessed by the trial statistician and the database manager.

The randomisation list will then be uploaded to the study database (REDCap). When a patient has been screened and has met all of the entry criteria in order to be eligible for trial participation, the unblinded investigator will go to the randomisation module on the database and complete the randomisation form. Once complete, the allocation (which is next in the sequence on the randomisation list) will be revealed to the unblinded investigator.

8 Patient Disposition

Participants will be those referred for either cardioversion for persistent AF (> 7 days) or catheter ablation of persistent AF. Inclusion/exclusion criteria are detailed in the protocol (section 7). Numbers of patients screened, excluded prior to randomisation by reason and overall, randomised and completing each phase of the study will be shown by treatment groups and overall following the Consort structure.

9 Demographics and Baseline characteristics

Demographic and baseline (screening data) will be:

1. Age
2. Sex
3. Ethnicity

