9. LVEF
10. Diabetes
11. Current Smoking
12. Hypertension
13. Hypercholesterolaemia
14. Previous MI
15. Previous PCI

Demographic and baseline data will be summarised by randomisation group and overall. For continuous data the number of subjects, mean, SD, median and interquartile range will be shown. For categorical data number and percentage will be shown. No formal testing will be performed for the comparison of baseline characteristics.

10 Interim analysis and timing for analysis.

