10.1 Interim analysis

On completion of the 6-week blinding period of the last patient to be enrolled into the pilot study, an interim analysis will be performed, including endpoints assessed from baseline to 6-weeks. No other interim analyses are planned prior to the completion of the study, unless specifically requested by the DSMC.

The main analysis will take place at the end of this pilot study and this information will be used to inform decisions regarding procedure to a main future trial. Patients will be followed up for 12 months regardless of interim analysis results.

10.2 Time points for analysis.

The DSMC will monitor patient safety and will meet prior to initiation of the study, after the recruitment of 4 patients and then at 3 monthly intervals. All other analysis described in this SAP will take place at the end of this pilot study.

11 Feasibility and Efficacy Analysis

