11.1.2 Analysis of efficacy endpoints

Categorical variables will be shown as the number with each endpoint and total number in each group along with the proportion. Odds ratios and 80% one-sided exact confidence intervals will also be shown as an assessment of efficacy, an approach described by Cocks et al⁴.

For continuous variables mean, SD, and number of patients with available data will be presented along with estimated mean difference between trial arms and 80% one-sided confidence intervals.

For AF burden (proportion of time in AF), median and IQR will also be reported.

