11.1.4 Covariate adjusted analysis

No covariate adjustment will take place.

11.2 Assumptions for analysis.

For continuous efficacy outcomes, confidence intervals for differences will be constructed assuming a normal distribution. Normality of distribution for continuous variables is hard to assess with such a small number of subjects in this pilot trial and so will not have much value.

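### The 12-month QoL difference is estimated as an unadjusted change score, and the baseline QoL scores, although collected, are neither adjusted for nor tabulated

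*SAP*

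**What the plan says.** SAP 6.4.5 fixes the endpoint: "Change in QOL will be measured by the change in AF-PROMS summary scores and SF-12 PCS and MCS between screening and 12 months". For continuous outcomes, SAP 11.1.2 reports the "estimated mean difference between trial arms and 80% one-sided confidence intervals", and SAP 11.1.4 states: "No covariate adjustment will take place". Table 4 has one row each for SF-12 MCS, SF-12 PCS and AF-PROMS, and each row shows the 12-month change only. SAP 6.5 gives the purpose of the limits: "to give an indication of whether the endpoint is likely to be of interest".

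Baseline QoL is available. On the screening visit, SAP 7.1.1 says: "Baseline characteristics, quality of life and symptom measures will be assessed at this point". SAP section 9 says of the baseline variables: "Demographic and baseline data will be summarised by randomisation group and overall". However, none of its 15 listed items is an SF-12 or AF-PROMS score, and Table 1 has no row for one. Ejection fraction, the other endpoint analysed as a change, does have its baseline value in both places. On allocation, SAP 7.4 says: "Randomisation will not be stratified by any factors".

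No other between-arm QoL estimate is defined. The 3-month scores appear only in the completeness table (Table 3). The interim analysis in SAP 10.1 is described as "including endpoints assessed from baseline to 6-weeks", which could cover 6-week QoL, but the section does not name QoL or specify a comparison.

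**The concern.** A change score uses the baseline, but it subtracts it with a coefficient fixed at 1. If the baseline/12-month correlation is below 1 and the SDs are similar, that over-corrects. The arm that happens to start lower is expected to gain more, whatever the treatment does. With 20 patients and no stratification, chance differences at baseline are large relative to any plausible effect. Because baseline QoL is in no planned table, a reader of Table 4 could not tell a treatment difference from regression to the mean.

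Two further points bear on the same score. The documents disagree on whether QoL is collected at 12 months. They are also unclear on when patients are told their arm, which matters for an outcome that protocol 12.3.1 singles out as especially open to placebo effects.

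**Working it through.** **The plan's own figure.** Protocol 11.1 states 80% power for 0.4 SD in any continuous variable with 104 per group at the 5% level. A two-sample t test gives 81.9%, and the effect detectable with 80% power is (1.960 + 0.842) × √(2/104) = 0.389 SD. The figure reproduces and is not in dispute. It concerns the main trial.

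**Inputs for the pilot.** n = 10 per arm (protocol synopsis; 20 in total in SAP 6.6), an 80% one-sided limit (SAP 6.5) and normal-theory intervals (SAP 11.2). The documents give no baseline/12-month correlation r, so I assume 0.3, 0.5 and 0.7, with equal SDs at the two times. All results are in SDs of the raw score.

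**Formulas.**
- Residual variance: 2(1 − r) for the change score and 1 − r² for ANCOVA. Their ratio is (1 + r)/2.
- Average ANCOVA penalty for chance imbalance: 1 + 1/(2n − 4) = 17/16.
- Distance to the limit, change score: t(0.80; 18) × √[2(1 − r) × 2/10], with t = 0.862.
- Distance to the limit, ANCOVA: t(0.80; 17) × √[(1 − r²) × 2/10 × 17/16], with t = 0.863.
- Baseline difference D (PVI arm minus DCCV arm): SE = √(2/10) = 0.447 SD. P(|D| > 0.447) is the chance of exceeding one SE, about 32%.
- Expected change-score difference given D, with no treatment effect: −(1 − r)D.

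| Assumed r | 0.3 | 0.5 | 0.7 |
|---|---|---|---|
| Variance ratio, (1 + r)/2 × 17/16 | 0.691 | 0.797 | 0.903 |
| Variance reduction | 31% | 20% | 10% |
| Change-score patients per arm that 10 with ANCOVA are worth (10/ratio) | 14.5 | 12.5 | 11.1 |
| Distance to limit, change score (SD) | 0.456 | 0.386 | 0.299 |
| Distance to limit, ANCOVA (SD) | 0.380 | 0.345 | 0.284 |
| Shift at D = −0.447 (SD) | 0.313 | 0.224 | 0.134 |
| Shift as a share of the change-score distance | 69% | 58% | 45% |

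Simulating 200,000 trials per value of r gave variance ratios of 0.692, 0.797 and 0.900. The two methods break even where (1 + r)/2 × 17/16 = 1, that is r = 32/17 − 1 = 0.88. With 9 per arm the distances are 0.482/0.408/0.316 for the change score and 0.403/0.366/0.302 for ANCOVA, so modest loss to follow-up does not alter the comparison.

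**Is QoL collected at 12 months?** The SAP schedule (6.4.3) marks QoL at screening, 6 weeks, 3 months and 12 months, and SAP 6.4.5 needs the last of these. The protocol schedule (9.4) marks QoL at screening, 6 weeks and 3 months only. SAP 7.1.1 gives the 12-month visit as clinical follow-up, ECG and symptoms. Both schedules list symptom questionnaires on a separate row, so the symptom mark at 12 months does not settle the matter.

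**When are patients told?** Protocol section 8 unblinds patient and physician once the patient's participation is complete, at 12 months. Protocol 12.3.1 withholds the allocation until the end of the trial period or the study end-point, whichever comes first. If study end-point means the end of participation, the two agree. If it means the patient's own recurrence, some patients would know their arm before giving the 12-month score. The protocol does not define the term.

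**The case against.** The best defence is that this is a pre-specified, legitimate choice in a small pilot. The change score is unbiased, no hypothesis is tested, the main objective is operational, and the progression criteria in protocol 11.2 set no QoL threshold. The gain depends on an assumed r and is slight at r = 0.7 (0.299 against 0.284 SD). Linearity would also be hard to check with 20 patients. All of this stands. It limits the point to precision and interpretation, but it does not explain why a baseline that is already collected is left out of the tables.

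Three stronger readings are tempting, and the documents do not support them.

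- A reader might infer that the QoL limits are misleading at a known error rate. Given a one-SE imbalance with the PVI arm lower and no true effect, a change-score limit would exclude zero in 37/35/31% of trials. But the SAP states no rule about excluding zero, and over all randomisations both methods sit at the nominal 20% or so.
- A reader might infer that many patients will know their arm by 12 months. That needs one particular reading of an undefined term, and disclosure at every recurrence. Protocol 9.6 withdraws patients who are accidentally unblinded, and 17.5 limits unblinding of individual patients by investigators to safety need. No count can be derived.
- A reader might infer that the lack of a blinding index after 3 months is a defect. Protocol 9.3.4 and SAP Table 2 stop there consistently. Guesses at 12 months would also reflect recurrence, so an index then would say little about blinding.

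The schedule mismatch may be partly a matter of versions: the SAP cites protocol version 2.0 of 25/06/2019, and the signatures in the protocol reviewed are dated 12 February 2019. The conflict between SAP 6.4.3 and SAP 7.1.1 does not depend on that.

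**Conclusion.** The point holds as a matter of precision and interpretability. The estimator is not biased and no stated figure is wrong. The documentary part is certain: the only defined QoL contrast is unadjusted, and baseline QoL is in neither SAP section 9 nor Table 1. The numerical part rests on the assumed r, equal SDs, a linear relation to baseline and about 10 evaluable patients per arm. On those assumptions ANCOVA saves 31% to 10% of the variance as r goes from 0.3 to 0.7, and nothing above about 0.88. An ordinary chance imbalance moves the planned estimate by 0.31 to 0.13 SD without being visible. The two conflicts over the 12-month visit and the time of unblinding are real gaps in the text, but their effect on the result cannot be sized from the documents.

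**What to change.** 1. Amend SAP 11.1.2 and 11.1.4 so that the 12-month differences in SF-12 PCS, SF-12 MCS and AF-PROMS are estimated by ANCOVA on the corresponding baseline score, with the same 80% one-sided interval. Keep the mean changes by arm in Table 4 as description. Cost: one degree of freedom and an assumed roughly linear relation to baseline.
2. Add the three baseline scores to SAP section 9 and Table 1. Cost: three rows from data already collected.
3. Reconcile the 12-month QoL assessment across the protocol schedule (9.4), SAP 7.1.1, SAP 6.4.3 and SAP 6.4.5.
4. Reconcile protocol sections 8 and 12.3.1 on when patients are told their arm, and define study end-point.

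Items 3 and 4 are text edits. Two additions are optional and purely descriptive: 3-month QoL differences labelled as supportive, and a repeat of the blinding question at 12 months before unblinding. The first adds three unadjusted intervals. The second would be imprecise, with an SE of about 0.22 to 0.32 at 10 per arm (√(share guessing/10), for half or all of the patients offering a guess).

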6.5 Level of significance

No hypothesis testing will be done for this pilot study.

For efficacy outcome measures we will use 80% one-sided confidence intervals to give an indication of whether the endpoint is likely to be of interest, an approach described by Cocks et al. for pilot trials⁴.

6.6 Sample size

The sample size of 20 subjects has been chosen as an achievable recruitment target that would enable assessment of feasibility of the study, and to confirm whether a larger trial could be conducted. At around 10% of a sample size required for a future main trial, this will also allow an initial assessment of the effectiveness of the intervention using a confidence interval approach⁴.

7 General Analysis Definitions

7.1 Study period and visit definitions

7.1.1 Visits

Patients will be identified as suitable for the study by their usual clinical care provider. Patients referred for DC cardioversion or management of persistent AF will be screened for inclusion into the trial. Patients will give informed consent in pre-admission. Baseline characteristics, quality of life and symptom measures will be assessed at this point.

On the day of the procedure patients will be randomised to DCCV or Pulmonary Vein Isolation plus DCCV. LINQ will be inserted during the procedure. Patients will be followed up at 6 weeks by telephone for quality of life and symptom measures.

Patients will return to the clinic at 3 months (clinical follow-up, 12 lead ECG, repeat QOL and symptom measures) and at 12 months (clinical follow-up, 12 lead ECG and symptoms). Monthly remote interrogation of the loop recorder will measure burden of AF (time in AF) and duration of episodes.

[figure not shown]
Patients who consent will remain within an observational registry for 5 years following the end of the trial. This long-term passive follow-up will track patient mortality and clinical status from

ORBITA-AF Pilot Trial: Statistical Analysis Plan

routinely collected clinical data. No intervention or investigations will be performed as part of this long term follow up.

Data from this pilot study will be analysed at 12 months to allow assessment of feasibility for a larger trial, and patients who complete the 12-month follow-up visit and consent will continue in registry follow-up for 5 years post procedure.

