7.2 Exclusion criteria

Patients who meet the following exclusion criteria will be ineligible for study participation;

- Creatinine clearance (eGFR) < 30mls/min
- Contraindication or unable to take anticoagulation
- Contraindication or unable to tolerate amiodarone
- Uncontrolled hypertension
- Contraindication or catheter ablation
- BMI > 35

8. Study design

Barts Health patients referred from other Barts Health NHS Trust Hospitals (Homerton, Chase Farm, Barnet) for either cardioversion for persistent AF or catheter ablation of persistent AF will be approached for recruitment.

- All patients:
 - Patient drug treatment will follow local clinical guidelines for AF ablation and be recorded in the CRF.
 - Patient baseline characteristics recorded at preadmission
 - Estimated AF duration
 - LA dimensions (Echocardiogram)
 - Ejection fraction
 - Routine Bloods

- Creatinine & Electrolytes,
- Full blood count,
- Thyroid function
- Quality of Life measures
- BP
- CHADS VASC score / assessment
- Medical History and Comorbidities
- Demographics (Age, sex, ethnicity)
- Physical exam (BP, HR, Weight, Height, BMI)
- Medications
- Day of Procedure – blinded randomisation to intervention (DCCV, or Pulmonary Vein Isolation plus DCCV). Reveal LINQ inserted during procedure.
- 6 weeks: QoL measures, telephone FU
- 3 months: Clinical follow up, 12 lead ECG, Repeat QOL measures
- 12 months: Clinical follow up, Endpoints measured. Once subject participation in the trial is complete, the patient and physician will be unblinded. If the patient is in AF, management of AF proceeds as clinically indicated.
- All patients who consent to have data capture continue in AF registry for 5 years.

The pilot study patients will be analysed at 3 months and 12 months to allow assessment of feasibility of a larger trial, and patients who complete the 12 month follow-up visit and consent will continue in registry follow-up for 5 years post procedure.

9. Study procedures

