9.4 Schedule of Assessment

Assessment	Screening/ pre-admission	Randomisation	Treatment/ Procedure	Implant	Recovery	6 weeks (telephone)	3 month (clinic)	12 month /EOS (clinic)	Monthly downloads	Registry
Visit window							+/- 7 days	+/- 2 weeks		
Informed consent	X									
Patient baseline characteristics recorded: estimated AF duration, LA dimensions (echo), LVEF, Bloods, Medications, Age, Sex, BP, CHADS VASC score, co-morbidities, demographics, weight, height, BMI.	X									
Randomisation		X								
DCCV only			X							
DCCV plus Pulmonary Vein Isolation			X							
Telephone FU						X				
Quality of life measures	X					X	X			
Clinical FU						X	X	X		
Loop recorder inserted				X						
12 lead ECG					X		X	X		
Interrogation of loop recorder				X			X	X	X	
Symptom questionnaires	X					X	X	X		
Clinical status and mortality data										X

The long term passive follow up will track patient mortality and clinical status from routinely collected clinical data. No intervention or investigations will be performed as part of this long term follow up.

9.5

Study Scheme Diagram

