16.3 Tools

16.3.1 Questionnaires:

Short Form (SF 12) The short form health survey

This is a shorter version of the SF-36 and consists of 12 questions. It is comparable with the SF-36 especially for the physical component summary (PCS) and mental component summary (MCS). This test gives more precision than the EQ-5D and has been extensively validated in general and also in cardiac populations (De Smedt, Clays, Annemans, & De Bacquer, 2014).

Atrial Fibrillation Specific Patient Reported Outcome Measure (AF PROMS)

This 28 item inventory measures how AF has impacted the patient's quality of life. It assesses how much the patient has been concerned by specific symptoms and how AF has impacted their emotional state and daily activities. This inventory was developed at Barts and has been validated by [name] (unpublished PhD thesis).

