13	Safety analysis.....	16
13.1	Adverse events (AE)	16
13.2	Deaths or serious adverse events (SAE)	16
14	Presentation of analysis	17
15	REFERENCES	23

4 GLOSSARY of Terms and Abbreviations

AE	Adverse event
AF	Atrial Fibrillation
BMI	Body Mass Index
BP	Blood Pressure
CHADS	Score for estimating AF stroke risk
CI	Confidence Interval
DBP	Diastolic Blood Pressure
DC	Direct Current
DCCV	Direct Current Cardioversion
DSMC	Data and Safety Monitoring Committee
ECG	Electrocardiogram
FU	Follow-up
HR	Heart Rate
IQR	Interquartile Range
LA	Left Atrial
LINQ	Reveal LINQ cardiac monitoring system
LVEF	Left Ventricular Ejection Fraction
MCS	Mental Health Composite Scale (SF-12)
MI	Myocardial infarction
BI	Blinding Index
OR	Odds Ratio
PCI	Percutaneous Coronary Intervention
PCS	Physical Health Composite Scale (SF-12)
PROMS	Patient Reported Outcome Measures
PVI	Pulmonary Vein Isolation
QoL	Quality of Life
R	“R” Statistical Programming Software
SAE	Serious Adverse Event
SAP	Statistical Analysis Plan
SF-12	Twelve item short form survey
SBP	Systolic Blood Pressure
SD	Standard Deviation

5 Introduction

This SAP has been written based on information from the study protocol version 2.0, dated 25/06/2019.

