6.4.2 Secondary endpoints

- Death within 12 months.
- Hospital re-admission for any reason.
- Procedural-related complications.
- Bleeding events within 7 days of procedure.
- Requirement for repeat procedures within 12 months.
- Change in ejection fraction.
- Clinical success of procedure.
- Change in quality of life, as measured by SF-12 and AF-PROMS at 12 months.
- AF burden as measured on continuous monitoring.
- Antiarrhythmic drug use within 12 months.

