DCCV + PCI	n12 (p12)	n22 (p22)	-
Don't know	n13 (p13)	n23 (p23)	-
Total	N1	N2	-
Blinding index	BI	BI	-

Table 3: Data completeness

	Treatment group		Total
	DCCV (N=)	DCCV +PVI (N=)	
Primary Endpoint data (Persistent AF)	N1 N2 % with data	N1 N2 % with data	N1 N2 % with data
SF12 3 months	N1 N2 % with data	N1 N2 % with data	N1 N2 % with data
12 months	N1 N2 % missing	N1 N2 % missing	N1 N2 % with data
AF-PROMS 3 months	N1 N2 % with data	N1 N2 % with data	N1 N2 % with data
12 months	N1 N2 % with data	N1 N2 % with data	N1 N2 % with data
Loop recorder interrogation performed			
3 months	N1 N2 % with data	N1 N2 % with data	N1 N2 % with data
12 Months	N1 N2 % with data	N1 N2 % with data	N1 N2 % with data
Patients completing all study assessments	N1 N2 % with data	N1 N2 % with data	N1 N2 % with data

N1= Number with data recorded

N2=Number with missing data

Table 4: Primary and Secondary Efficacy Endpoint analysis (ITT population)

	Treatment group		OR (80% CI)
	Placebo N=	Active N=	
Recurrent AF within 12 months	n/N (%)	n/N (%)	
Death within 12 months	n/N (%)	n/N (%)	
Hospital admission within 12 months	n/N (%)	n/N (%)	
Procedural-related complications	n/N (%)	n/N (%)	
Bleeding events within 7 days	n/N (%)	n/N (%)	
Requirement for repeat procedures within 12 months	n/N (%)	n/N (%)	
Clinical success of procedure	n/N (%)	n/N (%)	
AF drug use within 12 months	n/N (%)	n/N (%)	
	Placebo N=	Active N=	b (80% CI)
Change in ejection fraction at 12 months	Mean (SD)	Mean (SD)	
AF-Burden	Median [IQR] N Mean (SD)	Median [IQR] N Mean (SD)	
Change in QoL score at 12 months: SF-12 MCS	Mean (SD) N	Mean (SD) N	
SF-12 PCS	Mean (SD) N	Mean (SD) N	
AF-PROMS	Mean (SD) N	Mean (SD) N	

Table 5: Safety analysis – adverse events (safety population)

		Treatment group	
		Placebo N=	Active N=
Number of patients experiencing an AE within a year		n/N (%)	n/N (%)
Maximum severity AE experienced	Mild	n/N (%)	n/N (%)
	Moderate	n/N (%)	n/N (%)
	Severe	n/N (%)	n/N (%)
Total number of AEs across patients		n	n

Table 6: SAE listing

SAE number	Patient ID	SAE term (MedDRA)	SAE severity	Expected/ unexpected	Treatment group	Details of treatment	Related to treatment?
1							
2							
3							
4							
...							

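### SAP 7.1.1 and the supplied protocol schedule omit the 12-month quality-of-life forms that the SAP endpoint needs; adjusting that endpoint for its baseline is a cheap further gain in precision

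*SAP*

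**What the plan says.** **Endpoint.** SAP 6.4.2 lists "Change in quality of life, as measured by SF-12 and AF-PROMS at 12 months". SAP 6.4.5 defines it: "Change in QOL will be measured by the change in AF-PROMS summary scores and SF-12 PCS and MCS between screening and 12 months". SAP Table 4 has three rows for it, the first headed "Change in QoL score at 12 months: SF-12 MCS", and Table 3 counts completeness of both forms at 12 months. The SAP's own schedule (6.4.3) marks quality of life at 12 months.

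**Visits.** SAP 7.1.1 names quality of life and symptoms as separate items at screening, 6 weeks and 3 months. For the last visit it says "at 12 months (clinical follow-up, 12 lead ECG and symptoms". In the supplied Protocol 9.4 the row "Quality of life measures" is marked at screening, 6 weeks and 3 months only, while the symptom-questionnaire row is also marked at 12 months. Protocol section 8 names quality of life at 6 weeks and 3 months, then says "12 months: Clinical follow up, Endpoints measured".

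**Analysis.** SAP 11.1.2 gives the mean difference between arms with an 80% one-sided interval. SAP 11.1.4 rules out covariate adjustment for every endpoint.

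**Unblinding.** Protocol section 8 unblinds patient and physician once participation is complete. Protocol 12.3.1 has patients told at the earlier of the end of the trial period and the study end-point, and does not define the second term.

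**The concern.** Quality of life is part of the trial's hypothesis (Protocol 5.5.1) and comes first in the secondary objective (Protocol 6.2). Staff working from the supplied protocol schedule or from SAP 7.1.1 could reasonably omit the SF-12 at 12 months. A form missed then cannot be recovered on equal terms: Protocol section 8 unblinds at the end of participation, so a late form would be completed by a patient who knows the allocation. Blinding is there largely to protect outcomes of this kind (Protocol 12.3.1). Pilot patients may also be carried into the main trial (SAP 6.1), and the gap would go with them.

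The analysis question is smaller. SAP 6.5 uses the one-sided intervals to indicate whether an endpoint is likely to be of interest. With 10 patients per arm those intervals are wide, and the planned analysis uses the screening score only by subtracting it.

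The undefined term matters because one reading of it would allow disclosure before the 12-month forms are completed.

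**Working it through.** **1. Visit content side by side**

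| Place | Quality of life at 3 months | Quality of life at 12 months |
|---|---|---|
| SAP 7.1.1 | named, separately from symptoms | not named; symptoms only |
| Protocol 9.4 (supplied) | marked | not marked; symptom row marked |
| Protocol section 8 | named | not named; general statement on endpoints |
| SAP 6.4.3 | marked | marked |
| SAP 6.4.2 and 6.4.5 | not used | required |
| SAP Tables 3 and 4 | Table 3 rows | rows in both tables |

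Because SAP 7.1.1 keeps quality of life and symptoms apart at the other visits, its 12-month symptoms cannot safely be read as covering both. The conflict between SAP 7.1.1 and SAP 6.4.3 lies inside one document. The conflict between Protocol 9.4 and the SAP may not be real for the current protocol: the SAP says it is based on "study protocol version 2.0, dated 25/06/2019", whereas the signatures in the supplied protocol are dated 12 February 2019.

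If SAP 7.1.1 and the supplied Protocol 9.4 were followed literally, the SF-12 MCS, SF-12 PCS and AF-PROMS rows of Table 4 and the two 12-month rows of Table 3 would be empty. AF-PROMS might still be given as a symptom questionnaire, since Protocol 16.3.1 says of it: "It assesses how much the patient has been concerned by specific symptoms". In that case the two SF-12 rows of Table 4 and one row of Table 3 remain exposed. Carried into the main trial, the gap would affect 20/208 = 9.6% of patients.

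**2. Value of baseline adjustment**

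The only related figure in the plan is in Protocol 11.1: 104 per group gives 80% power for 0.4 SD. A two-sample t test at two-sided 5% gives 81.9%, so the statement reproduces, and nothing here changes it.

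Inputs for the pilot: n = 10 per arm (Protocol section 4; 1:1 allocation in SAP 7.4). Assumptions: the score has the same SD, set to 1, at screening and 12 months, and the two are correlated r in both arms. The documents give no r, so a range is shown.

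- Change-score SE = √[2(1 − r) × 2/10]
- Adjusted SE = √[(1 − r²) × (2/10) × (1 + 1/16)]. The last factor is the cost of estimating the slope with 20 patients.
- Distance from the estimate to the 80% one-sided limit = SE × t, with t = 0.862 on 18 df (change) and 0.863 on 17 df (adjusted).

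At r = 0.5: √(2 × 0.5 × 0.2) = 0.447 against √(0.75 × 0.2 × 1.0625) = 0.399, and 1 − 0.399/0.447 = 10.7%.

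| Assumed r | Change SE | Adjusted SE | SE reduction | Distance to limit, change | Distance to limit, adjusted |
|---|---|---|---|---|---|
| 0.3 | 0.529 | 0.440 | 17% | 0.456 | 0.380 |
| 0.5 | 0.447 | 0.399 | 11% | 0.386 | 0.345 |
| 0.7 | 0.346 | 0.329 | 5% | 0.299 | 0.284 |
| 0.8 | 0.283 | 0.277 | 2% | 0.244 | 0.239 |
| 0.9 | 0.200 | 0.201 | none | 0.172 | 0.173 |

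Break-even: (1 + r)/2 × 17/16 = 1 gives r = 15/17 = 0.88. A simulation of 40,000 trials at r = 0.3, 0.5 and 0.7 agreed with these SEs to within 0.001. Both estimators had a mean error below 0.003 SD, so neither is biased.

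**3. The undefined term**

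The study end-point in Protocol 12.3.1 could mean the patient's own 12-month completion. That precedes the last patient's visit, which ends the study (Protocol 9.8), and it agrees with Protocol section 8. It could also mean first recurrence, since the sentences that follow turn to reversion to persistent AF. That reading sits badly with section 8, with Protocol 9.6 (accidentally unblinded patients are withdrawn) and with Protocol 17.5 (individual unblinding only where safety requires it).

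**The case against.** **Collection.** The SAP asks for 12-month quality of life in its endpoint list, schedule, definition and tables. The outlier within the SAP is one parenthesis in a narrative. Protocol section 8 says endpoints are measured at 12 months, Protocol 6.4 gives its quality-of-life endpoint no time point, and the scheme diagrams are not in the supplied text. All of this stands. A reader might infer that no patient will have 12-month scores; the documents do not support that. They support a contradiction to remove and a risk of loss.

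**Adjustment.** The absence of adjustment is a stated choice in a 20-patient pilot with descriptive aims (SAP 6.2) and no hypothesis tests (SAP 6.5). That also stands. A reader might infer that the planned comparison is biased or invalid, but under randomisation it is neither. The gain rests on an assumed r and is slight when r is high: at r = 0.7 the limit moves by about 0.015 SD. No pilot decision is shown to turn on it. Deleting SAP 11.1.4 outright would leave AF burden and the binary endpoints without a rule, so only an exception is warranted.

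**Unblinding.** A reader might infer that patients are told their allocation at first recurrence, and might use the planning rates of 66% and 47% to count them. The text does not establish that reading. Those rates are for recurrence of AF within one year, not for episodes longer than 7 days counted outside the 6-week blanking period (SAP 6.4.5). Protocol 9.3.1 also keeps patients blinded to their ECG and rhythm. No count of early disclosures is justified.

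**Conclusion.** The point holds in three parts of unequal weight.

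- **Main part.** SAP 7.1.1 contradicts the rest of the SAP on 12-month quality of life, and the supplied protocol schedule has the same gap. This is certain as a matter of text for the SAP. For the protocol it depends on which version governs. The consequence is a risk of losing up to three Table 4 rows and two Table 3 rows, for an outcome named in the hypothesis. It should be corrected before 12-month visits take place.
- **Second part.** Baseline adjustment is a low-cost improvement, not the repair of an error. It shortens the SE by 2% to 17% for r between 0.8 and 0.3, with nothing gained from about 0.88, assuming equal SDs at the two times and a linear relation.
- **Minor part.** One term in Protocol 12.3.1 needs a definition. No amount of early unblinding or bias is claimed.

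**What to change.** 1. Confirm which protocol version governs. Name SF-12 and AF-PROMS at 12 months in SAP 7.1.1, Protocol section 8 and Protocol 9.4, and state that they are completed before the unblinding described in section 8. Cost: one SAP sentence, one protocol line and one schedule cell. If the governing protocol has the same gap, the change goes to the ethics committee as an amendment (Protocol section 12).

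2. Keep SAP 11.1.4 for all other endpoints and add an exception: the arm difference in 12-month SF-12 PCS, SF-12 MCS and AF-PROMS is estimated by linear regression on arm plus the screening score, with the planned 80% one-sided interval. Keep unadjusted mean change (SD) in Table 4. Cost: one SAP paragraph and one degree of freedom per analysis (18 to 17).

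3. Define study end-point in Protocol 12.3.1 and reconcile that section with Protocol sections 8, 9.6 and 17.5. Which rule should apply is for the investigators; none is proposed here. Cost: one defined term.
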